## 11.6 Safety Oversight

The study Medical Monitor will review all adverse events that are reported during the study. SAEs will typically be reviewed within 24-hours of reporting. Other AEs will typically be reviewed approximately weekly.

A Data and Safety Monitoring Board (DSMB) will be informed of all cases of severe hypoglycemia and diabetic ketoacidosis irrespective of device relationship and all UADEs during the study and will review compiled safety data at periodic intervals. The DSMB also will be informed of any SAEs and ADEs not meeting criteria for a UADE if the Medical Monitor requests the DSMB review. The DSMB can request modifications to the study protocol or suspension or outright stoppage of the study if deemed necessary based on the totality of safety data available. Details regarding DSMB review will be documented in a separate DSMB Charter.

## 11.7 Stopping Criteria

### 11.7.1 Participant Discontinuation of Study Participation

In the case of a UADE, use of the study device will be suspended while the problem is diagnosed. After assessment of the problem and any correction, use of the study device will not be restarted until approval is received from the IRB, DSMB, and FDA.

Use of the study device by a participant will be discontinued if any of the following occur:

- The investigator believes it is unsafe for the participant to continue on the intervention. This could be due to the development of a new medical condition or worsening of an existing condition; or participant behavior contrary to the indications for use of the device that imposes on the participant's safety.
- The participant requests that the treatment be stopped
- Participant pregnancy
- Two distinct episodes of DKA as defined above
- Two distinct severe hypoglycemia events as defined above
- One episode of DKA and one severe hypoglycemia event as defined above

An additional requirement for continued study device use following a single DKA or severe hypoglycemia event will be that (1) the site investigator believes that the event is explainable, unlikely to recur, and that it is safe for the participant to continue to use the system and (2) the Medical Monitor concurs. If the Medical Monitor determines that the occurrence of the event indicates that it is not safe for the participant to continue to use the system, use will be discontinued, and the subject will be withdrawn from the study.

### 11.7.2 Criteria for Suspending or Stopping Overall Study

Stopping criteria for the entire study will be determined by an independent DSMB, who will assess the specific event rates for DKA and severe hypoglycemia from

the study at specific timepoints relative to published rates from large, population-based datasets.

In consideration of adverse events rates occurring in this proposed the rates will be assessed relative to published rates from Foster et. al. and Miller et. al. to determine whether severe hypoglycemia or diabetic ketoacidosis are within expected rates during this study. **Table 6: T1D Exchange Rates of Severe Hypoglycemia and Diabetic Ketoacidosis** provides a summary of these published rates.

**Table 6: T1D Exchange Rates of Severe Hypoglycemia and Diabetic Ketoacidosis**

Adverse Event	Frequency of subjects to experience $\geq 1$ event extrapolated from T1DX registry 2016-2018, 2013-2014
Severe hypoglycemia (loss of consciousness or seizure)	4-5% < 18 years 7% $\geq 18$ years
Diabetic ketoacidosis (overnight hospitalization)	3-4% < 18 years 2-3% $\geq 18$ years

For unanticipated adverse device effects (UADEs), the DSMB will determine whether the study should proceed or not based upon risk of additional serious adverse events and the underlying root cause analysis of the UADE.

Study activities could be similarly suspended if the manufacturer of any component of the investigational study device requires stoppage of device use for safety reasons (e.g. product recall).

The affected study activities may resume if the underlying problem can be corrected by a protocol or system modification that will not invalidate the results obtained prior to suspension.

The study Medical Monitor will review all adverse events that are reported during the study, and the DSMB will review all cases of severe hypoglycemia, DKA and UADEs as well as compiled safety data at periodic intervals. The Medical Monitor and/or DSMB may recommend suspension of study activities or stoppage of the study to the Sponsor if deemed necessary based on the totality of safety data available.

## 11.8 Data Safety Monitoring Board (DSMB)

The DSMB will be established prior to the first enrollment and consist, at a minimum, of two physicians and one statistician independent from the Sponsor and study. The physicians will have relevant therapeutic and medical expertise. The DSMB will determine the stopping criteria for the entire study and review Severe Hypoglycemia and DKA as well as compiled safety data at periodic intervals to determine if the stopping rules apply. Compiled safety data may include listings of protocol deviations, device deficiencies, subject terminations, and subject withdrawals. In addition, the DSMB members will be notified upon the occurrence of any UADEs to determine whether the study should proceed or not.

based upon risk and may request an ad hoc meeting to discuss. At minimum, the DSMB will conduct reviews after 16 subjects from the prepivotal study have completed a minimum of 10-days of hybrid closed-loop and at the conclusion of the prepivotal study. Further reviews will occur during the pivotal study, as defined, in the pivotal study protocol. Additional reviews during the study may be conducted at any time based on the request of the DSMB, Sponsor or Medical Monitor. At the conclusion of each meeting, the DSMB will make a recommendation to the Sponsor concerning the continuation, modification, and/or termination, of the study and/or a statement regarding their overall assessment of device safety and continuation of the pivotal study. The final decision regarding the continuation, modification or termination of the study will reside with the Sponsor. Responsibilities, qualifications, membership and committee procedures, including the final stopping rules, will be outlined in the DSMB Charter.

### **11.9 Medical Monitor**

An independent Medical Monitor will be responsible for individual and timely review of adverse events as defined below. The Medical Monitor will be a physician with relevant therapeutic and medical expertise that is not participating as an Investigator in the study and does not have a financial, scientific, or other conflict of interest with the clinical study.

Specific responsibilities of the Medical Monitor include:

- Review of all adverse events reported during the study
- Review all serious study procedure-related and/or investigational device-related adverse events to determine if the adverse event warrants consideration as a UADE and facilitate the reporting of UADEs if applicable
- Adjudicate the following(a) all SAEs; (b) any events of Diabetic Ketoacidosis or Severe Hypoglycemia; (c) all AEs reported by the site as related or possibly related to the investigational device; and/or (d) any additional events as requested by the Sponsor or DSMB.
- The specified events will be adjudicated to determine:
  - event relatedness to the study procedures and/or the investigational device
  - event categorization and assess seriousness and severity
  - whether an adverse event is anticipated or unanticipated

The adjudication decision of the Medical Monitor will be used for the final classification of events, including relatedness to the study procedures and/or the investigational device, for the determination of safety endpoints and for all regulatory reports, product labeling, and publications or presentations.

The Medical Monitor's roles and responsibilities are described in the Safety Management Plan (SMP).

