### 5.1 MEDICAL MONITOR

An independent Medical Monitor will be responsible for individual and timely review of adverse events. The Medical Monitor will also adjudicate all serious adverse events (SAEs), including events of severe hypoglycemia and diabetic ketoacidosis, as well as all device-related adverse events for seriousness, severity, relationship to study device and procedure, whether the event is anticipated or unanticipated, and event categorization. The adjudication decision by Medical Monitor will be used for the final classification of adverse events for regulatory reports, product labeling, and publications or presentation.

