## 7.2 CONTROL OF SYSTEMATIC BIAS

Several measures are incorporated into the study design to help minimize study bias as follows:

- 1) This is a multi-center trial to help ensure that investigator or site or subject enrollment bias is minimized. Selection of subjects will be made from the Investigator's usual subject load. Consecutively eligible subjects should be enrolled into the study.
- 2) This document specifies appropriate statistical methodology to ensure that bias is minimized.
- 3) The effectiveness measures will be based on the direct output from the device, ensuring objective reporting.
- 4) An independent Medical Monitor will adjudicate all SAEs and device related adverse events; the Medical Monitor's assessment of adverse events will be used for regulatory reports, product labeling, and publications or presentation.

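### By default, Medical Monitor adjudication can lower but not raise the site's count of non-serious device-related adverse events

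*Protocol*

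**What the plan says.** Under Protocol 11.3.5 the investigator first rates each AE as unrelated, possibly related or related. Protocol 11.9 then names four groups that the Medical Monitor adjudicates. Two enter whatever the site's causality rating: every SAE, as item (a), together with "b) any events of Diabetic Ketoacidosis or Severe Hypoglycemia". A third group, item (c), enters only on the strength of that rating: "all AEs reported by the site as related or possibly related to the investigational device". The last rests on a request: "d) any additional events as requested by the Sponsor or DSMB". Adjudication settles relatedness, category, seriousness, severity and whether the event was anticipated. On its standing, 11.9 says: "The adjudication decision of the Medical Monitor will be used for the final classification of events". This extends to safety endpoints, regulatory reports and labeling.

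Review is a separate and wider duty. Protocol 11.6 states: "The study Medical Monitor will review all adverse events that are reported during the study". Section 11.9 repeats this among the Monitor's responsibilities. Neither section says that review alone can change a classification.

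SAP 5.1 describes the adjudicated set as all SAEs, "as well as all device-related adverse events for seriousness, severity, relationship to study device and procedure". SAP 7.2 lists the process among the measures that limit bias: "An independent Medical Monitor will adjudicate all SAEs and device related adverse events". Neither SAP section contains item (d), and neither says whose rating makes an event device-related. SAP 1 gives the SAP precedence over the protocol on any discrepancy. SAP 5.4 tabulates AEs by seriousness and by relationship to the device, among other factors, and SAP 5.2 counts possibly related as related.

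**The concern.** For a non-serious event, entry to adjudication depends on the very rating that adjudication is meant to check. A site rating of related is tested and may be overturned. A site rating of unrelated normally stands without an independent ruling. A check that looks at one kind of error only is not neutral, yet SAP 7.2 presents it as a bias control.

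One exposed class of event is prolonged hyperglycemia with raised ketones. Protocol 11.3.4 makes it reportable and generally not serious. Protocol 11.2 names occlusion and a dislodged cannula as causes to consider, so device causality is a live question. If a site attributes such an event to something else, nothing in 11.9 (a) to (c) brings it to the Monitor for a ruling.

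At stake is the reported number of non-serious device-related AEs, in a study whose stated purpose includes the safety of the device.

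**Working it through.** The documents give no expected AE count and no accuracy for site or Monitor, so there is no stated figure to reproduce. The check has two parts: the routes as written, and an illustration in which every input is assumed.

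**1. Routes as written**

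| Event as rated by the site | Default adjudication? | Which way can the rating move? |
|---|---|---|
| SAE, DKA or severe hypoglycemia, any relatedness | Yes, (a) or (b) | Either way |
| Non-serious, related or possibly related | Yes, (c) | Relatedness down or unchanged; seriousness may be raised |
| Non-serious, unrelated | No; only on request under (d) | Unchanged by default, for both relatedness and seriousness |

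**2. Formulas**, for N = 100 reported non-serious AEs. Let p be the share truly device-related, Se and Sp the site's sensitivity and specificity, and a and b those of the Monitor.

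- True count: T = 100p
- Site count: S = 100[p·Se + (1 − p)(1 − Sp)]
- Final count under (c) alone: F = 100[p·Se·a + (1 − p)(1 − Sp)(1 − b)]
- Added if a share q of site-unrelated events is referred under (d): 100q[p(1 − Se)a + (1 − p)·Sp·(1 − b)]

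Since a and 1 − b are at most 1, F cannot exceed S. This bound needs no assumed values.

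**3. Accurate Monitor (a = b = 1).** F = 100·p·Se, so the relative error is F/T − 1 = Se − 1. For Se of 0.95, 0.90, 0.80 and 0.70 it is −5%, −10%, −20% and −30%.

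Example with p = 0.30, Se = 0.80, Sp = 0.90:

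- S = 100(0.30 × 0.80 + 0.70 × 0.10) = 24 + 7 = 31, against T = 30.
- F = 24.
- The site missed 30 × 0.20 = 6. Referring 25% of site-unrelated events under (d) recovers 0.25 × 6 = 1.5, giving 25.5. Adjudicating all events gives 30.

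**4. Other assumed inputs**

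| p, Se, Sp, a, b | True | Site | Final, (c) alone | All adjudicated |
|---|---|---|---|---|
| 0.30, 0.80, 0.90, 1, 1 | 30 | 31 | 24 | 30 |
| 0.30, 0.80, 0.90, 0.95, 0.95 | 30 | 31 | 23.15 | 32 |
| 0.30, 1, 0.80, 1, 1 | 30 | 44 | 30 | 30 |
| 0.30, 1, 0.80, 0.95, 0.50 | 30 | 44 | 35.5 | 63.5 |
| 0.10, 0.90, 0.80, 0.95, 0.70 | 10 | 27 | 13.95 | 36.5 |

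For example, row four is 30 × 0.95 + 14 × 0.50 = 28.5 + 7 = 35.5. Over 384 assumed combinations (p 0.1 to 0.5, Se and Sp 0.7 to 1, a 0.9 to 1, b 0.5 to 1), the final count under (c) alone was below the truth in 269, above it in 92 and equal in 23. These tallies depend on the values chosen and are not probabilities.

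**5. Endpoints touched.** The primary safety endpoint counts serious device-related AEs. The secondary ones are severe hypoglycemia and DKA, which Protocol 11.3.3 and 11.3.4 treat as SAEs. All of these enter under (a) or (b) whatever the site's causality rating.

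**The case against.** The strongest reply has four parts.

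- **An upward route exists.** A reader might infer that adjudication can never add a device-related event. Item (d) says otherwise. It also has sources to draw on: the Monitor reviews every AE, the DSMB sees compiled safety data (Protocol 11.8), and the Sponsor reviews controller data (Protocol 12.5, SAP 7.8). The Safety Management Plan, which is not among the documents, may state a referral rule. This stands, so the point is limited to the default process. But (d) is discretionary, the request belongs to the Sponsor or DSMB and not to the Monitor, and Protocol 11.6 contains no rule that notifies the DSMB of a non-serious event rated unrelated. The SAP's silence on (d) may be mere abbreviation or, given its precedence clause, a narrowing; the documents do not settle which.
- **Default adjudication may still improve accuracy.** In the first example the site misclassifies 6 + 7 = 13 of 100 events. After default adjudication 6 remain wrong. The site total of 31 lies near 30 only because its two kinds of error nearly cancel. This stands, and it rules out saying that the process is generally worse than the site's own ratings.
- **Sites may seldom miss an event.** The possibly-related category in Protocol 11.3.5 has a low threshold and counts as related, which favours over-attribution. This is fair. The miss rate is unknown and may be small.
- **The consequence is modest.** AE analysis is descriptive (SAP 5.4), SAP 2.5 sets no success criteria, and all AEs are listed. This stands. A listing shows a site-unrelated event but gives no independent ruling on it.

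**Conclusion.** The point holds as a one-sided default. For non-serious AEs, the process in Protocol 11.9 (a) to (c) and SAP 5.1 and 7.2 corrects over-attribution but not under-attribution, and the final device-related count is capped at the site's count unless a discretionary request is made under (d).

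A reader might go further and infer that the reported count must lie below the truth. The documents do not support that. It follows if the Monitor is accurate and sites miss some events, with a shortfall equal to the miss rate. If the Monitor upholds some of the site's false positives, the count can exceed the truth, as in the 35.5 against 30 above.

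Nor does the primary safety endpoint become unreliable through this route, since site-reported SAEs are adjudicated whatever their causality rating. What remains there is small: an event the site rates both non-serious and unrelated receives no default ruling on seriousness either, so it has no set path into that endpoint.

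This is a cheap improvement to descriptive safety tables, not a threat to the study's main safety result.

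**What to change.** Reword item (c) of Protocol 11.9, and the matching text in SAP 5.1 and 7.2, so that the Medical Monitor records a relatedness and seriousness classification for every reported AE whatever the site's rating. State in SAP 5.4 that the tables by relationship and seriousness use this classification, and show the site's rating beside it so that moves in both directions can be seen. The side-by-side display matters: full adjudication by a Monitor who attributes events too readily can overshoot (63.5 against 30 in the fourth row above), and the display would expose that.

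The cost is wording in two documents and some more adjudication entries in a study of at most 48 subjects. The same Monitor already reviews every reported AE. The device-related count may come out higher. A smaller change, repeating item (d) in the SAP with a stated trigger, would make the upward route explicit but would leave the default filter in place.

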## 12 STATISTICAL CONSIDERATIONS

### 12.1 Objectives and Endpoints

#### 12.1.1 Safety Objective

The safety objective of the study is to evaluate the safety of the Omnipod Horizon™ System in patients with type 1 diabetes.

##### 12.1.1.1 Primary Safety Endpoint

Proportion of subjects with serious device-related adverse events.

##### 12.1.1.1 Secondary Safety Endpoints

- Proportion of subjects with severe hypoglycemia during hybrid closed-loop
- Proportion of subjects with diabetic ketoacidosis (DKA) during hybrid closed-loop

#### 12.1.2 Primary Effectiveness Objective

The primary effectiveness objective of this study is to evaluate the effectiveness of the Omnipod Horizon™ System

##### 12.1.2.1 Primary Effectiveness Endpoints

The primary effectiveness objective will be evaluated by comparing the percentage of time in range (70-180 mg/dL) during hybrid closed-loop compared to the standard therapy for:

- Target BG challenge days (approximately hybrid closed-loop days 1-9)
- Non-challenge days (approximately hybrid closed-loop days 10-14)
- Overall (hybrid closed-loop days 1-14)

#### 12.1.3 Secondary Effectiveness Objective

The secondary objective of the study is to evaluate additional glycemic measures of effectiveness of the Omnipod Horizon™ System.

#### 12.1.4 Secondary Effectiveness Endpoints

The secondary objective will be evaluated using the following per subject endpoints:

- Glucose metrics from system CGM during the hybrid closed-loop phase will be compared to the standard therapy phase during the day, overnight, and overall:
  - Mean glucose

- % of time in range 70-180 mg/dL
- % of time in range 70-140 mg/dL
- % of time > 180 mg/dL
- % of time  $\geq$  250 mg/dL
- % of time  $\geq$  300 mg/dL
- % of time < 70 mg/dL
- % of time < 54 mg/dL
- Standard deviation
- Coefficient of variation

- GMI based on overall mean glucose
- Percentage of time in hybrid closed-loop as proportion of overall device usage time
- Insulin requirements during the hybrid closed-loop phase will be compared to the standard therapy phase:
  - Total daily insulin (TDI) (units, units/kg)
  - Total daily basal insulin (units, units/kg)
  - Total daily bolus insulin (units, units/kg)

## 12.2 Sample Size

This is a single-arm, multi-center, prospective study. The sample size is not hypothesis-driven and was chosen to provide adequate information on the device's safety and performance.

## 12.3 Analysis Sets

The following analysis sets are planned for the study:

### 12.3.1 ITT (Intention to Treat) Analysis Set

The ITT analysis set includes all subjects that are enrolled in the study. All safety analyses (other than primary analysis of primary safety endpoints) will be based on the ITT analysis set.

### 12.3.2 mITT (modified Intention to Treat) Analysis Set

The modified Intention to Treat (mITT) analysis set is a subset of the ITT analysis set. The mITT analysis set will consist of subjects who have entered the hybrid closed-loop phase of the study successfully. The mITT analysis set will be used as the primary analysis for the primary and secondary endpoints and other clinical outcome data.

### 12.3.3 PP (Per-Protocol) Analysis Set

The Per-Protocol (PP) analysis set is a subset of the mITT analysis set. Subjects will be included in the PP analysis set if they have a minimum of 80% system use during the hybrid closed-loop phase inclusive of Manual and Automated Modes over a duration of 14-days and have completed the study without major protocol

deviations. The PP analysis set will be used as supportive analysis for the effectiveness endpoints. The following will be considered major protocol deviations:

- Major inclusion/exclusion criterion deviation
- Significant protocol non-compliance that may confound the study objective data (e.g., use of prohibited medications)

The list of subjects excluded from the PP analysis set will be determined prior to analysis. If the PP analysis set does not differ from the mITT analysis set, separate analyses will not be presented.

#### **12.4 Analysis of Primary and Secondary Effectiveness Endpoints**

Summary statistics will be presented by age cohort for all endpoints, stratified by time points of interest (e.g., day vs. night, overall). The effectiveness endpoints will be summarized for modified Intention to Treat (mITT) and Per Protocol (PP) analysis sets. If the PP analysis set does not differ from the mITT analysis set, separate analyses will not be presented. The data may be stratified by phase of the study, where the data collected in the standard therapy phase of the study (after adjustment of parameters, if necessary) will be compared to the data collected in the hybrid closed-loop phase of the study. The primary effectiveness endpoint will also be presented by existing Dexcom G6 use at the time of screening (users and non-users).

The primary effectiveness endpoint and the secondary effectiveness endpoints that summarize time in specific glycemic ranges will be calculated from device data outputs as follows:

$$100 \times \frac{\# \text{ of CGM records in range}}{\# \text{ of evaluable CGM records}} = TIR\%$$

All statistical comparisons will be conducted at a two-side significance level of 5%. Since the results of endpoint analyses are not used to support clinical claims, no adjustment for multiplicity will be included. Data from all sites will be pooled for all analyses; no separate analyses by site or formal testing of poolability will be performed.

